APPENDIX D: PATIENT-REPORTED OUTCOMES SURVEYS (PARTS A AND B US PATIENTS ONLY)

NCI PRO-CTCAE

Item Library Version 1.0

English

Form created on 06 July 2018

As individuals go through treatment for their cancer they sometimes experience different symptoms and side effects. For each question, please check or mark an in the one box that best describes your experiences over the past 7 days.

1.	In the last 7 days, how OFTEN did you have NAUSEA?				
	 Never	 Rarely	 Occasionally	 Frequently	 Almost constantly
1a.	In the last 7 days, what was the SEVERITY of your NAUSEA at its WORST?				
	 None	 Mild	 Moderate	 Severe	 Very severe
2.	In the last 7 days, how OFTEN did you have VOMITING?				
	 Never	 Rarely	 Occasionally	 Frequently	 Almost constantly
2a.	In the last 7 days, what was the SEVERITY of your VOMITING at its WORST?				
	 None	 Mild	 Moderate	 Severe	 Very severe
3.	In the last 7 days, what was the SEVERITY of your CONSTIPATION at its WORST?				
	 None	 Mild	 Moderate	 Severe	 Very severe
4.	In the last 7 days, how OFTEN did you have LOOSE OR WATERY STOOLS (DIARRHEA/DIARRHOEA)?				
	 Never	 Rarely	 Occasionally	 Frequently	 Almost constantly
5.	In the last 7 days, how OFTEN did you have PAIN IN THE ABDOMEN (BELLY AREA)?				
	 Never	 Rarely	 Occasionally	 Frequently	 Almost constantly
5a.	In the last 7 days, what was the SEVERITY of your PAIN IN THE ABDOMEN (BELLY AREA) at its WORST?				
	 None	 Mild	 Moderate	 Severe	 Very severe

5b.	In the last 7 days, how much did PAIN IN THE ABDOMEN (BELLY AREA) INTERFERE with your usual or daily activities?				
	 Not at all	 A little bit	 Somewhat	 Quite a bit	 Very much
6.	In the last 7 days, what was the SEVERITY of your NUMBNESS OR TINGLING IN YOUR HANDS OR FEET at its WORST?				
	 None	 Mild	 Moderate	 Severe	 Very severe
6a.	In the last 7 days, how much did NUMBNESS OR TINGLING IN YOUR HANDS OR FEET INTERFERE with your usual or daily activities?				
	 Not at all	 A little bit	 Somewhat	 Quite a bit	 Very much
7.	In the last 7 days, what was the SEVERITY of your BLURRY VISION at its WORST?				
	 None	 Mild	 Moderate	 Severe	 Very severe
7a.	In the last 7 days, how much did BLURRY VISION INTERFERE with your usual or daily activities?				
	 Not at all	 A little bit	 Somewhat	 Quite a bit	 Very much
8.	In the last 7 days, what was the SEVERITY of your WATERY EYES (TEARING) at their WORST?				
	 None	 Mild	 Moderate	 Severe	 Very severe
8a.	In the last 7 days, how much did WATERY EYES (TEARING) INTERFERE with your usual or daily activities?				
	 Not at all	 A little bit	 Somewhat	 Quite a bit	 Very much
9.	In the last 7 days, did you BRUISE EASILY (BLACK AND BLUE MARKS)?				
	 Yes	 No			
10.	In the last 7 days, how OFTEN did you have NOSEBLEEDS?				
	 Never	 Rarely	 Occasionally	 Frequently	 Almost constantly
10a.	In the last 7 days, what was the SEVERITY of your NOSEBLEEDS at their WORST?				
	 None	 Mild	 Moderate	 Severe	 Very severe
Do you have any other symptoms that you wish to report?					
	 Yes	 No			

Please list any other symptoms:

1.	In the last 7 days, what was the SEVERITY of this symptom at its WORST?				
	 None	 Mild	 Moderate	 Severe	 Very severe
2.	In the last 7 days, what was the SEVERITY of this symptom at its WORST?				
	 None	 Mild	 Moderate	 Severe	 Very severe
3.	In the last 7 days, what was the SEVERITY of this symptom at its WORST?				
	 None	 Mild	 Moderate	 Severe	 Very severe
4.	In the last 7 days, what was the SEVERITY of this symptom at its WORST?				
	 None	 Mild	 Moderate	 Severe	 Very severe
5.	In the last 7 days, what was the SEVERITY of this symptom at its WORST?				
	 None	 Mild	 Moderate	 Severe	 Very severe

Other questions to be asked weekly (same schedule as PRO-CTCAE questions):

1. I am bothered by the side effects of treatment:
 - a. Not at all
 - b. A little bit
 - c. Somewhat
 - d. Quite a bit
 - e. Very much
2. How much difficulty do you have doing work or hobbies that require you to see well up close?
 - a. No difficulty at all
 - b. A little difficulty
 - c. Moderate difficulty
 - d. Extreme difficulty
 - e. Stopped doing this because of your eyesight
3. Do you have difficulty seeing colors?
 - a. No difficulty at all
 - b. A little difficulty
 - c. Moderate difficulty
 - d. Extreme difficulty
 - e. Stopped doing this because of your eyesight
4. How much difficulty do you have driving at night?
 - a. No difficulty at all
 - b. A little difficulty
 - c. Moderate difficulty
 - d. Extreme difficulty
 - e. Stopped doing this because of your eyesight

PROMIS® Item Bank v2.0 – Physical Function – Short Form 6b

Physical Function – Short Form 6b

Please respond to each question or statement by marking one box per row.

		Without any difficulty	With a little difficulty	With some difficulty	With much difficulty	Unable to do
PFA11	Are you able to do chores such as vacuuming or yard work?	 5	 4	 3	 2	 1
PFA21	Are you able to go up and down stairs at a normal pace?	 5	 4	 3	 2	 1
PFA23	Are you able to go for a walk of at least 15 minutes?	 5	 4	 3	 2	 1
PFA53	Are you able to run errands and shop?	 5	 4	 3	 2	 1
		Not at all	Very little	Somewhat	Quite a lot	Cannot do
PFC12	Does your health now limit you in doing two hours of physical labor?	 5	 4	 3	 2	 1
PFB1	Does your health now limit you in doing moderate work around the house like vacuuming, sweeping floors or carrying in groceries?	 5	 4	 3	 2	 1

APPENDIX E: PERFORMANCE STATUS SCALES CONVERSION

Karnofsky		Lansky		ECOG	
Percent	Description	Percent	Description	Score	Description
100	Normal, no complaints, no evidence of disease.	100	Fully active, normal.	0	Normal activity. Fully active, able to carry on all pre-disease performance without restriction.
90	Able to carry on normal activity; minor signs or symptoms of disease.	90	Minor restrictions in physically strenuous activity.		
80	Normal activity with effort; some signs or symptoms of disease.	80	Active, but tires more quickly.	1	Symptoms, but ambulatory. Restricted in physically strenuous activity, but ambulatory and able to carry out work of a light or sedentary nature (e.g., light housework, office work).
70	Cares for self, unable to carry on normal activity or to do active work.	70	Both greater restriction of, and less time spent in, play activity.		
60	Requires occasional assistance, but is able to care for most of his/her needs.	60	Up and around, but minimal active play; keeps busy with quieter activities.	2	In bed <50% of the time. Ambulatory and capable of all self-care, but unable to carry out any work activities. Up and about more than 50% of waking hours.
50	Requires considerable assistance and frequent medical care.	50	Gets dressed, but lies around much of the day; no active play; able to participate in all quiet active play and activities.		
40	Disabled, requires special care and assistance.	40	Mostly in bed, participates in quiet activities.	3	In bed >50% of the time. Capable of only limited self-care, confined to bed or chair more than 50% of waking hours.
30	Severely disabled, hospitalization indicated. Death not imminent.	30	In bed, needs assistance even for quiet play.		
20	Very sick, hospitalization indicated. Death not imminent.	20	Often sleeping, play entirely limited to very passive activities.	4	100% bedridden. Completely disabled. Cannot carry on any self-care. Totally confined to bed or chair.
10	Moribund, fatal processes progressing rapidly.	10	No play, does not get out of bed.		
0	Dead.	0	Dead.	5	Dead.

APPENDIX F: GUIDANCE ON CONTRACEPTION

For the purposes of this guidance, complete abstinence, if consistent with the subject's preferred lifestyle, is an acceptable form of contraception. Complete abstinence is defined as abstinence starting from the time of informed consent and continuing throughout the study and until the end of systemic exposure (at least 6 months after the final dose of study drug; see Section **Error! Reference source not found.**).

Acceptable methods for highly effective birth control (preventing conception)

Subjects who are of childbearing potential^a or whose partners are of childbearing potential^a and who are sexually active in a way that could lead to pregnancy may choose any TWO of the following methods (please see acceptable combinations below):

- Hormonal methods of contraception (excluding progestin-only pills; method must be associated with inhibition of ovulation), unless contraindicated
- Intrauterine device with failure rate <1%
- Tubal ligation
- Barrier method (male or female condom with or without spermicide, cervical cap with or without spermicide, diaphragm with or without spermicide)^b

a A person of childbearing potential is defined as anyone born female who has experienced menarche and who has not undergone surgical sterilization (e.g., hysterectomy, bilateral salpingectomy, bilateral oophorectomy) or has not completed menopause. Menopause is defined clinically as 12 months of amenorrhea in a person born female over age 45 in the absence of other biological, physiological, or pharmacological causes.

b A barrier method should only be used with a highly effective birth control method that is not a barrier method. Barrier methods alone, including a double-barrier method, are not considered highly effective contraceptive measures (see unacceptable methods of contraception).

Acceptable combinations of contraceptive methods:

- Hormonal method and barrier method
- Intrauterine device and barrier method
- Tubal ligation and barrier method

Unacceptable methods of contraception

- Periodic abstinence
- No method
- Withdrawal
- Rhythm
- Spermicide only
- Progestin-only pills
- Concomitant use of female and male condoms
- Barrier methods alone, including double-barrier methods

APPENDIX G: RECIST CRITERIA SUMMARY (VERSION 1.1)

Response Evaluation Criteria in Solid Tumors	
Term	Definition
Complete response (CR)	Disappearance of all target lesions. Any pathological lymph nodes must have reduction in short axis to <10 mm.
Partial response (PR)	At least a 30% decrease in the sum of diameters of target lesions, taking as reference the baseline sum diameters.
Progressive disease (PD)	At least a 20% increase in the sum of diameters of target lesions, taking as reference the smallest sum on study (this includes the baseline sum if that is the smallest on study). In addition to the relative increase of 20%, the sum must also demonstrate an absolute increase of at least 0.5 cm. The appearance of one or more new lesions is also considered progression.
Stable disease (SD)	Neither sufficient shrinkage to qualify for PR nor sufficient increase to qualify for PD, taking as reference the smallest sum diameters while on study.
Measurable lesion	Must be accurately measured in at least one dimension (longest diameter in the plane of measurement is to be recorded) with a minimum size of 10 mm by CT scan (CT slice thickness no greater than 5 mm).

From RECIST Version 1.1 ([Eisenhauer 2009](#))

A response (CR or PR) will be considered confirmed if the following disease assessment (at least 4 weeks after the initial response) still shows response (CR or PR). In cases where the initial response is followed by SD, it will be considered as confirmed if the SD is later followed by PR or CR. For example, if a patient had PR in week 6, SD in Week 12, and PR in Week 18, this PR will be considered as confirmed.

APPENDIX H: NEW YORK HEART ASSOCIATION CLASSIFICATION

A Functional and Therapeutic Classification for Prescription of Physical Activity for Cardiac Patients

- Class I: patients with no limitation of activities; they suffer no symptoms from ordinary activities.
- Class II: patients with slight, mild limitation of activity; they are comfortable with rest or with mild exertion.
- Class III: patients with marked limitation of activity; they are comfortable only at rest.
- Class IV: patients who should be at complete rest, confined to bed or chair; any physical activity brings on discomfort and symptoms occur at rest.

On-line source: http://www.heart.org/HEARTORG/Conditions/HeartFailure/AboutHeartFailure/Classes-of-HeartFailure_UCM_306328_Article.jsp

APPENDIX I: CALCULATION OF PREDICTIVE PROBABILITY OF SUCCESS

1. Let N_{max} be the maximum sample size of a cohort, and n be the number of patients treated and evaluated for the response status by the time of interim analysis
2. Assume the prior distribution of the response rate p follows a beta distribution

$$p \sim \text{beta}(a_0, b_0)$$

Note: A weakly informative prior with $a_0 = 0.12$ and $b_0 = 0.88$ is chosen for this study to reflect the prior belief of 12% ORR with tisotumab vedotin, and let the data speak for itself so that inferences are not overly affected by information external to the observed data.

3. Let X be the number of responders in the first n patients, and X follows a binomial distribution

$$X \sim \text{binomial}(n, p)$$

The likelihood function for the observed data x is $L(p \mid X = x) \propto p^x (1-p)^{n-x}$

4. With the Bayes theorem, the posterior distribution of the response rate given $X = x$ follows a beta distribution

$$p \mid x \sim \text{beta}(a_0 + x, b_0 + n - x)$$

5. Let Y be the number of responders in the potential m future patients, where $m = (N_{max} - n)$, thus Y follows a beta-binomial distribution

$$Y \sim \text{beta-binomial}(m, a_0 + x, b_0 + n - x)$$

Given $Y = i$, the posterior distribution of p follows $\text{beta}(a_0 + x + i, b_0 + N_{max} - x - i)$

6. Let $B_i = \Pr(p > p_0 \mid x, Y = i)$, where B_i measures the probability that the response rate p exceeds p_0 (the response rate of current stand of care), given x responders in the first n patients and i responders in the m future patients
7. Compare B_i to a threshold value θ_T . If $B_i > \theta_T$, then the cohort is considered “success” at the end of the cohort given the interim data and the potential outcome of $Y = i$.

Note: A more relaxed threshold value, $\theta_T = 70\%$, is chosen for this study given the exploratory nature of study.

$$PPoS = \sum_{i=0}^m \{\Pr(Y = i \mid x) \cdot I(\Pr(p > p_0 \mid x, Y = i) > \theta_T)\} = \sum_{i=0}^m \{\Pr(Y = i \mid x) \cdot I(B_i > \theta_T)\}$$

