- Interim futility analysis performed on Part B after at least 20 patients with 1 to 3 prior lines of therapy, including bevacizumab treatment, have been treated and had at least one response assessment post-baseline. The interim futility analysis will ensure that further enrollment of these patients has reasonable potential to provide clinically meaningful benefit from tisotumab vedotin. While the futility analysis is being performed, enrollment in Part B will continue.

The feasibility of targeting TF in ovarian cancer with tisotumab vedotin has been demonstrated in the clinic in phase I studies in heavily pretreated populations with encouraging activity results. Preliminary safety and activity data from the GEN701 and GEN702 trials suggest a positive benefit-risk profile and warrant further investigation of tisotumab vedotin in ovarian cancer populations that exhibit high unmet medical need.

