3 INVESTIGATIONAL PLAN

3.1 Summary of Study Design

This is an open-label, phase 2 study with an initial safety run-in period. The safety run-in period will evaluate the safety of a dose-dense schedule and will start at a 0.9 mg/kg dose level. If 0.9 mg/kg is considered safe and tolerable, the dose level will be escalated to 1.2 mg/kg. Otherwise it will be de-escalated to 0.65 mg/kg. Each dose level will enroll approximately 6 patients. Patients who do not complete the DLT period will be replaced. A

dose level is considered safe and tolerable if no more than 1 patient experiences a DLT among 6 patients during the DLT period. The highest dose level that is considered safe will be the recommended phase 2 dose (RP2D) and will be used in Part A. If no RP2D for the dose-dense schedule is identified, Part A will be a single arm of the Q3W regimen and Part B will not enroll.

In Part A, 60 patients will be randomized in a 1:1 ratio to receive tisotumab vedotin 2.0 mg/kg intravenously (IV) every 3 weeks (Q3W regimen) or the safety run-in RP2D on Days 1, 8, and 15 of every 4-week cycle (dose-dense regimen; 3Q4W) if a RP2D has been identified. Randomization will be stratified by first line vs. second line PROC and histology (serous vs. non-serous).

Based upon antitumor activity and safety data, one Part A treatment arm may be expanded to enroll up to an additional 70 patients to further characterize safety and antitumor activity of tisotumab vedotin for patients with PROC. The analysis to support expansion will be conducted when approximately 30 patients per arm have at least one post-baseline response assessment per RECIST v1.1 or have discontinued from the study or started subsequent cancer therapy.

Part B will enroll approximately 80 patients with PROC including approximately 60 patients who have received 1 to 3 prior lines of therapy, including bevacizumab treatment. Part B will further characterize the long-term efficacy, safety, and PK assessments of 0.9 mg/kg tisotumab vedotin on Days 1, 8, and 15 of every 4-week cycle (dose-dense regimen) if the 0.9 mg/kg dose level is considered safe and tolerable in the safety run-in period. Enrollment in this cohort may discontinue when Part A begins enrollment.

[figure not shown]

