9.2 Study Endpoint Definitions

9.2.1 Confirmed ORR

Confirmed ORR is defined as the proportion of patients who achieve a confirmed CR or PR according to RECIST v1.1 as assessed by the investigator. Patients who do not have at least 2 post-baseline response assessments (initial response and confirmation scan) will be counted as non-responders.

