9.3.9 Interim Analyses

A safety analysis will be conducted at end of DLT period for each dose level in the safety run-in portion to evaluate the tolerability of dose-dense regimen. A SMC consisting of the investigators, study medical monitor, biostatistician, and drug safety representative will review the data before proceeding to Part A.

Interim analysis for futility will be performed on Part B after at least 20 patients with 1 to 3 prior lines of therapy, including bevacizumab treatment, have been treated and had at least one response assessment post-baseline.

The Bayesian predictive probability approach will be used to determine the futility criteria (Lee 2008). At the time of the interim futility analysis, the PPoS will be calculated. PPoS is the probability of achieving “success” should the cohort be continued to the maximum sample size of 60 in the target population (1 to 3 prior lines of therapy, including bevacizumab treatment) given the data observed at interim, and the cohort is considered “success” if the posterior probability that the ORR exceeds the response rate of current standard of care (i.e., 12% as reference in Section 3.2) is greater than 70%.

Both the confirmed and unconfirmed CR or PR observed at interim will be counted as a response for the calculation of PPoS. It is appropriate to include the unconfirmed response for the purpose of interim analysis because based on the estimates from GEN701 trial, about 60% of the responders will respond at their first post-baseline scan and approximately 75% of the confirmed/unconfirmed responses will eventually be confirmed. Table 9 summarizes the PPoS based on the number of responses observed among the first 20 patients. Details of the calculation of PPoS are shown in Appendix I.

Table 9: PPoS based on responses among the first 20 patients pretreated with bevacizumab

No. of responses* among the first 20 patients	PPoS
	PROC bevacizumab pretreated ($p_0=12\%$)
0	<1%
1	4%
2	20%
3	49%
4	77%
5	93%
6	99%
7	>99%
8	>99%
9	>99%
10+	>99%

* P_0 is the response rate of current standard of care of each cohort

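### The Part B futility look leaves treated patients with no post-baseline scan out of n and models them as future possible responders, although the final ORR counts them as non-responders

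*Protocol*

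**What the plan says.** Protocol 9.3.9 (also 3.1 and 9.3.1.9, and SAP 4 and 8) times the Part B interim by at least 20 target patients who "have been treated and had at least one response assessment post-baseline". Appendix I defines n as "the number of patients treated and evaluated for the response status by the time of interim analysis", and PPoS then projects to the cohort "continued to the maximum sample size of 60 in the target population", with m = 60 − n: "Let Y be the number of responders in the potential m future patients". Neither text says how a treated patient with no post-baseline scan enters the calculation.

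The final analysis is explicit. ORR is computed on the full analysis set, which is everyone who received any study drug (protocol 9.3.1.7, SAP 5.1). For the confirmed rate, protocol 9.2.1 states: "Patients who do not have at least 2 post-baseline response assessments (initial response and confirmation scan) will be counted as non-responders". Section 9.2.2 likewise counts patients with no post-baseline assessment as non-responders in the rate that includes unconfirmed responses, the type of response used at the interim.

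The Part A expansion look is worded differently. Its trigger, at roughly 30 in each arm, covers those who "have at least one post-baseline response assessment per RECIST v1.1 or have discontinued from the study or started subsequent cancer therapy". The protocol's efficacy-evaluable set (9.3.1.7) carries a similar clause. The Part B futility wording does not.

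**The concern.** The interim conditions on reaching a scan and the final endpoint does not. A target patient lost before any scan is a known non-responder for the final analysis. At the interim that patient drops out of n and, if one of the 60, reappears among the m future patients with a positive predicted chance of response. Both effects raise PPoS for a given number of responses.

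Protocol 1.4 lists this look among the measures taken to keep patients safe and says: "The interim futility analysis will ensure that further enrollment of these patients has reasonable potential to provide clinically meaningful benefit from tisotumab vedotin". PPoS is the only quantitative criterion that the plan gives the sponsor for that decision. If it is computed on a different population from the final ORR, Table 9 and the fixed rule of at most 1 response in 20 do not describe the analysis they are meant to predict.

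**Working it through.** **Inputs.** Prior beta(0.12, 0.88), N = 60, reference rate 12% and posterior threshold 70% (Appendix I and 9.3.9). The futility line is PPoS below 10% and the upper line is above 70% (9.3.9). The number k of treated target patients without a scan is not given; I use 0 to 6.

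**Formula (Appendix I).** PPoS = sum over i = 0..m of Pr(Y = i) × I[Pr(p > 0.12) > 0.70], where m = 60 − n, Y ~ beta-binomial(m, 0.12 + x, 0.88 + n − x), and p ~ beta(0.12 + x + i, 0.88 + 60 − x − i).

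**Final success boundary.** 8 of 60 gives a posterior probability of 58.6% and 9 of 60 gives 72.5%. Success therefore needs at least 9 of 60.

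**Reproducing the plan.** At n = 20, x = 0 to 6 gives 0.07%, 3.75%, 19.6%, 48.6%, 77.2%, 93.4% and 98.9%. This agrees with Table 9. The futility column of Table 10 is Pr(X ≤ 1) for binomial(20, p): 73.6%, 39.2%, 17.6%, 6.9% and 2.4% at p = 5% to 25%, again in agreement.

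**Counting k unscanned patients as non-responders** (n = 20 + k, x unchanged, N = 60):

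| k | k/(20 + k) | PPoS, x = 2 | PPoS, x = 4 |
|---|---|---|---|
| 0 | 0% | 19.6% | 77.2% |
| 1 | 4.8% | 16.8% | 73.6% |
| 2 | 9.1% | 14.3% | 69.8% |
| 3 | 13.0% | 12.1% | 65.9% |
| 4 | 16.7% | 10.2% | 61.9% |
| 5 | 20.0% | 8.5% | 57.7% |
| 6 | 23.1% | 7.0% | 53.6% |

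With 2 responses the 10% line is crossed at k = 5, not at k = 4. With 4 responses the 70% line is crossed at k = 2.

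**Sensitivity to the meaning of 60.** If the 60 were all scanned patients and the k came on top (N = 60 + k), x = 2 would give 9.8% at k = 3. Section 9.3.9 fixes 60 as the maximum in the target population, so the table above follows the text.

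**Effect on stopping probability, this component alone.** Suppose the ORR among all treated patients is 10% and a share d is never scanned. The rate among scanned patients is 0.10/(1 − d), which is 11.1% at d = 10% and 12.5% at d = 20%. Pr(X ≤ 1 of 20) falls from 39% to 33% and 27%. At an all-treated ORR of 5% it falls from 74% to 69% and 64%.

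**How often a decision would change.** At a true ORR of 10%, let unscanned patients accrue until 20 have been scanned. The chance of k ≥ 5 together with exactly 2 responses is about 0.2%, 2.4% and 7.9% for early loss of 5%, 10% and 15%. At 10% loss, for example, this is Pr(k ≥ 5) × Pr(x = 2) = 0.085 × 0.28 = 0.024.

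**The opposing component.** Section 9.3.9 says that about 60% of responders respond at their first scan and that about 75% of confirmed or unconfirmed responses are eventually confirmed. In the extreme case where every patient has had one scan only, the look sees 0.60 of eventual responders and the final analysis counts 0.75, a ratio of 0.60/0.75 = 0.80. Leaving out 20% unscanned patients inflates the rate by 1/0.80 = 1.25, and 1.25 × 0.80 = 1.00.

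**The case against.** A reader might infer that the look as a whole is biased towards continuing. The documents do not support that. As the last step of the working shows, responses still to come after a first scan pull PPoS down, and in the extreme case this cancels a 20% loss. That case is an upper bound, since earlier patients will have had more scans. It is still enough to leave the net direction open.

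A reader might also infer that every early drop-out is excluded. The protocol narrows the group:

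- Patients who stop treatment stay on study (4.4.1), and imaging continues off treatment unless they have progressed or started other therapy (7.2).
- Imaging is due whenever progression is suspected (7.2). It is also part of the end-of-treatment visit, which must precede new therapy and waives the scan only if one was done in the previous 4 weeks (6.6).
- Entry requires ECOG 0 or 1 and a life expectancy of at least 3 months (4.1).

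What remains is mainly early deaths and consent withdrawals.

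The wording can also be read as fixing only when the look takes place. Protocol 9.3.1.7 puts all efficacy analyses on the full analysis set, so a statistician might already count unscanned patients as non-responders. That reading is possible, but Appendix I's definition of n and the missing Part A clause point the other way, and the text should not leave it to choice.

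Finally, the stop is non-binding and is weighed with safety data. PFS and OS are reviewed at the same look, which brings early deaths into view. These points limit the consequence. They do not make n match the final population.

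**Conclusion.** The mismatch is real on the text. The interim n omits treated target patients without a scan, the model treats them as possible future responders, and the final ORR counts them as non-responders. Considered alone, the omission raises PPoS.

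Its effect on the decision is modest. With N fixed at 60 and no more than 6 unscanned patients, the 10% line is crossed only with exactly 2 responses and at least 5 unscanned patients, or 20% or more of those treated. A reader might infer that one interim result can cross both PPoS lines. It cannot over the range examined: the 10% line is crossed at 2 responses and the 70% line at 4. The plan attaches no action to the 70% line, so the fall from 77.2% to 69.8% changes no stated decision.

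All of this rests on an assumed number of unscanned patients. A net bias towards continuing is not established. The change is worth making because it corrects a stated decision rule at almost no cost.

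**What to change.** In protocol 9.3.1.9, 9.3.9 and Appendix I and in SAP 8, define the interim set as the first 20 or more treated target patients, in order of first dose, who have had at least one post-baseline response assessment or have died, discontinued from the study or started subsequent cancer therapy. Count those without a scan as non-responders. Ordering by first dose matters, because early losses reach a known status sooner than patients still waiting for a scan.

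Compute PPoS on the actual n and apply the rule of PPoS below 10%, rather than the fixed count of at most 1 in 20, whenever n exceeds 20. With the Appendix I inputs, the largest number of responses that gives PPoS below 10% is 1 for n = 20 to 24 and 2 for n = 25 to 31.

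The cost is wording in the SAP and in the protocol at its next amendment, with no new patients or data. PPoS will be slightly less favourable when early losses occur, and the look may be reached slightly earlier.
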